3.1.9 Patient must provide study specific informed consent prior to study entry

- 3.1.10 Prior breast augmentation, including breast implants, is allowed
- 3.1.11 Patients with a prior history of contralateral breast cancer will be considered eligible if they completed all treatment (including anti-endocrine therapy) more than 2 years prior to registration
- 3.1.12 Patients must not have a prior treatment of malignancy diagnosed or treated within the past two years, with the exception of non-melanomatous skin cancer, carcinoma in situ of the cervix and contralateral breast cancer as described in 3.1.11.
- 3.1.13 Interested patients must meet with a medical oncologist prior to study entry to determine if a genomic profiling tests (such as Oncotype or MammaPrint) is recommended. If recommended and patient is amenable to the possibility of receiving chemotherapy, there must be adequate biopsy tissue for testing. If adequate tissue is not available for the testing, patients who are very interested in participation may undergo additional biopsies. If a patient plans to refuse chemotherapy regardless of a high profiling results and elects to forgo the test, they will still be eligible for enrollment.

3.2 Conditions for Patient Ineligibility

- 3.2.1 AJCC clinical T3, N1-3, M1, stage IIB, stage III or stage IV breast cancer
- 3.2.2 Prior invasive non-breast malignancy (exceptions include non-melanomatous skin cancer, carcinoma in situ of the cervix, or prior contralateral breast cancer as described in 3.1.11) unless disease free and off treatment for a minimum of 5 years prior to study entry.
- 3.2.3 Multifocal breast cancer

- 3.2.4 Estrogen receptor negative disease
- 3.2.5 Lymphovascular space invasion noted on biopsy
- 3.2.6 Invasive lobular carcinoma
- 3.2.7 Purely non-invasive breast cancer (i.e. ductal carcinoma in situ (DCIS), lobular carcinoma in situ). Note: DCIS is often associated with invasive ductal carcinoma. Associated DCIS does NOT preclude eligibility as long as there is invasive carcinoma on the biopsy specimen.
- 3.2.8 Non-epithelial breast malignancies such as sarcoma or lymphoma
- 3.2.9 Paget's disease of the nipple
- 3.2.10 Male breast cancer
- 3.2.11 Prior history of radiation therapy to the chest in the region of the ipsilateral breast that would result in overlap of radiation fields.
- 3.2.12 Patients having received or having planned neoadjuvant chemotherapy or concurrent chemotherapy. A recommendation for adjuvant chemotherapy will not preclude eligibility. However, if a patient has an Oncotype score that would lead to a recommendation for systemic chemotherapy (see section 3.1.13), and chemotherapy is planned to be given in the neoadjuvant setting, the patient would then be ineligible for enrollment.
- 3.2.13 Patients who are unable to undergo MRI. This could include patients with a severe allergy to gadolinium contrast or patients with renal function insufficient to receive contrast (GFR less than 30). Patients who have a minor allergy (for example, skin rash or hives) to gadolinium contrast may still be considered for enrollment. These patients would have to receive prophylactic prednisone and diphenhydramine per MCW department of radiology protocol. Such cases should be reviewed with the principal investigator and radiology co-chair prior to enrollment.

3.2.14 History of connective tissue disorder, including lupus, dermatomyositis and scleroderma

3.2.15 Known BRCA mutation

3.2.16 Severe, active co-morbidity, defined as follows:

- Unstable angina and/or congestive heart failure requiring hospitalization within the last 6 months
- Transmural myocardial infarction within the last 6 months
- Acute bacterial or fungal infection requiring intravenous antibiotics at the time of registration;
- Chronic Obstructive Pulmonary Disease exacerbation or other respiratory illness requiring hospitalization or precluding study therapy within 30 days before registration;
- Hepatic insufficiency resulting in clinical jaundice and/or coagulation defects; note, however, that laboratory tests for liver function and coagulation parameters are not required for entry into this protocol
- Acquired Immune Deficiency Syndrome (AIDS) based upon current CDC definition; note, however, that HIV testing is not required for entry into this protocol. The need to exclude patients with AIDS from this protocol is necessary because the treatments involved in this protocol may be significantly immunosuppressive

3.2.17 Medical, psychiatric or other condition that would prevent the patient from receiving the protocol therapy or providing informed consent

3.2.18 Patients, who under the best estimates of the treating radiation oncologist, have a life expectancy of 10 years or less

3.2.19 Patients who are pregnant

4.0 Pre- and Post-Treatment Evaluation and Management

Note: This section lists baseline evaluations needed before the initiation of protocol treatment that do not affect eligibility. For specific studies that affect eligibility, please see section 3.0.

4.1 Required Pre-Treatment Evaluations/Management

4.1.1 Patients must complete forms and have photos taken for cosmetic evaluation on the study

4.1.2 Bone scan or any other staging work-up for patients when warranted based on symptoms or at the discretion of the treating physicians should be completed prior to enrollment. Similarly, work up of abnormal labs or physical exam findings should all be completed prior to enrollment.

4.2 Required Post-Treatment Evaluations/Management

4.2.1 Patients will be seen one month after radiation treatment and evaluated for acute side effects of treatment. Breast exam from this visit will be documented.

4.2.2 A post-radiation MRI scan will be obtained no sooner than 28 days after completion of radiation therapy. This scan must be obtained prior to surgery.

4.2.3 Advanced MRI imaging sequences performed for simulation will be obtained on the post-treatment scan. These are described in more detail in section 6.1.9 below.

4.2.4 Tumor response will be assessed using the RECIST and mRECIST criteria (64). Also, changes in the MRI sequences detailed in section 6.1.9 will also be assessed. The baseline measurements for this analysis will be taken from the MR

sim and not from any diagnostic MRI the patient may have had prior to radiation planning.

- 4.2.5 Blood draw for future studies of immune markers (see section 9.1.3). These will be done prior to radiation treatment, at the end of radiation (+/- 1 treatment) and then one month after radiation treatment but prior to surgery.

5.0 Registration Procedures

5.1 Registration and Monitoring of Patients

- 5.1.1 Patients will be screened for eligibility and registered by a Clinical Research Associate/Clinical Research Coordinator (CRC/CRA) in the Clinical Trials Office of the Froedtert and Medical College of Wisconsin Cancer Center.
- 5.1.2 Patients will be registered in the institutional OnCore web-based system under the CRA console.
- 5.1.3 Registration of patients with consenting, eligibility review, on-study status, treatment status, and follow-up will be monitored using the OnCore calendar system.
- 5.1.4 Serious adverse events (SAEs) and protocol deviations will be reported through the OnCore reporting system.
- 5.1.5 Questions regarding OnCore systems and data reporting should be reported to OnCore data management.

5.3 Subject Withdrawal

- 5.3.1 Given the short nature of the treatment regimen (radiation is given over 1.5-2 weeks), and very low rates of toxicity during radiation treatment, it is unlikely that patients will withdraw from the study once radiation treatment has begun. However, subjects have the right to withdraw from the study at any time.
- 5.3.2 Subjects may be withdrawn from the study if a subject's status declines and in the opinion of the treating physicians it is in the subject's best interest to be withdrawn. Subjects may also be withdrawn if there is a violation of the protocol inclusion and exclusion criteria as deemed relevant by the treating physician and the principal investigator.
- 5.3.3 It is anticipated that the most likely reason for a subject withdrawal will be for those not suitable for APBI based on radiation treatment planning (see Section 6.4 and 6.4.2 below for further details). As these patients would be withdrawn prior to delivery of study related treatment, they will then be replaced on the study and not counted toward the total accrual goal of 40 patients. Similarly, patients withdrawing for any other reason prior to delivery of treatment will be replaced on the study and not counted toward the total accrual goal.
- 5.3.4 In the rare case that a patient withdraws from the protocol after the initiation of treatment, only data collected up until the date of withdrawal will be used in analysis. If the withdrawal occurs during radiation therapy, data will only be included in analysis of the primary study endpoint if a post-operative complication occurs.
- 5.3.5 Patients who withdraw from the study should be treated in accordance with normal standards of care. Follow-up will be per the discretion of the patient's treating physicians, but at a minimum be in accordance with NCCN guidelines.

Management of disease recurrence or any unforeseen late morbidity of treatment will be managed by the treating physicians.

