2.2 Secondary

- 2.2.1 Measure rates of breast fibrosis and pain for patients treated with APBI and compare with historical controls of patients treated with post-operative APBI.
- 2.2.2 Collect data on cosmetic outcomes for patients treated with pre-operative APBI
- 2.2.4 Measure rates of need for re-excision because of a close or positive margin after pre-operative APBI.
- 2.2.5 Record long term outcomes of local recurrence rates and overall survival of patients treated with this modality.
- 2.2.6 Demonstrate the feasibility of MRI-based treatment planning for pre-operative APBI and compare dosimetric data from treatment planning with patients treated on a previous institutional post-op APBI protocol.
- 2.2.7 Study changes in MRI imaging from pre-treatment evaluation, treatment planning, and pre-surgical imaging and correlate those changes to pathological response.
- 2.2.8 Measure changes in tumor gene expression and immune response to radiation therapy and correlate this with pathologic response.

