10.0 Patient Assessments

10.1 Study Parameters

- 10.1.1 See Appendix 1 for a summary of assessments and time frames
- 10.1.2 Breast assessments will be conducted during radiation therapy with one ideally occurring on the last day of treatment
- 10.1.3 A breast exam must be conducted by a Physician, Physician Assistant or Nurse Practitioner at clinic visits and documented 42 days prior to study entry, 4-6 weeks post radiation, prior to surgery, no later than one month after the last surgery (post-operative visit), six months after surgery, 12 months after surgery (+/- 2 months) and then annually until 5 years after treatment is completed. The annual follow-up interval of 12 months +/-2 months will be calculated from the actual date of the last follow-up visit.
- 10.1.4 Post-operative complications (the primary endpoint of the study) will be defined as any complication occurring within 3 months of surgery. These may include but are not limited to: post-operative infection requiring oral/IV antibiotics (CTCAE grade 2 or higher), need for hospital re-admission due to surgical complications, wound dehiscence (CTCAE grade 2 or higher), significant hematoma at the operative site requiring drainage (CTCAE grade 2 or higher), and persistent symptomatic seroma formation that will be defined as need for seroma drainage or need for pain medications because of seroma formation (CTCAE grade 2 or 3), or any need for re-operation excluding re-excision for concerns related to resection margin.
- 10.1.5 At follow-up visits (see Appendix I for schedule), documentation will be made of disease status (no evidence of disease, local recurrence, regional recurrence, or distant recurrence) and toxicity. Toxicity will be graded according to CTCAE v4.0.

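### Physician withdrawal of a treated patient ends the use of her data, which can bias late outcomes favourably and, in a narrow window, the primary endpoint

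*Combined protocol and SAP*

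**What the plan says.** The combined protocol and SAP gives two grounds for withdrawal by physicians in 5.3.2. The first is "Subjects may be withdrawn from the study if a subject's status declines", joined to a second condition: the treating physicians must think that withdrawal is in her best interest. The other ground reads "Subjects may also be withdrawn if there is a violation of the protocol inclusion and exclusion criteria as deemed relevant by the treating physician". That judgement is shared with the principal investigator. Neither ground carries a time limit.

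Section 5.3.4 covers withdrawal after treatment has started, which it expects to be rare: "only data collected up until the date of withdrawal will be used in analysis". It adds one rule for withdrawal during radiation: "data will only be included in analysis of the primary study endpoint if a post-operative complication occurs". Section 5.3.5 then says "Follow-up will be per the discretion of the patient's treating physicians", with a guideline minimum for clinical care. No section keeps a withdrawn patient in study follow-up.

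The outcomes affected are:
- the primary endpoint in 10.1.4, "any complication occurring within 3 months of surgery";
- objective 2.2.5, "Record long term outcomes of local recurrence rates and overall survival of patients treated with this modality";
- fibrosis, pain and cosmesis, with follow-up visits to five years (10.1.3).

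Section 11.2 plans Kaplan-Meier or cumulative incidence estimates for local control, cosmetic outcomes, fibrosis and pain.

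**The concern.** Those estimates assume that a censored patient has the same outlook as one still followed. Withdrawal because a patient is declining breaks that assumption, and the bias runs in the favourable direction. Section 11.2 has no sensitivity analysis for it.

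The eligibility ground raises a different problem. These patients need not be the sickest. But whether a violation is relevant is a matter of judgement, made by staff who know the treatment and may know the outcome, in an open single-arm study. A treated patient could be taken out after her result is visible.

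The primary decision turns on single events: 7 complications in 39 (17.9%) is success and 8 in 39 (20.5%) is not.

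**Working it through.** **1. Which withdrawals are exposed.** Reading 5.3.2, 5.3.4 and 10.1.4 together:
- Before treatment: the patient is replaced (5.3.3), so no treated patient's outcome is lost.
- During radiation: a post-operative complication is still counted (5.3.4). That primary-endpoint event is not lost.
- After radiation, with the complication already recorded: the event is kept, because data up to withdrawal are used.
- After radiation, with a first complication later but within 3 months of surgery: the event is lost to the primary endpoint.
- At any time after treatment starts, with a later recurrence, late toxicity or death: the event is lost to the secondary outcomes.

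**2. The plan's own design figures (11.1).** Inputs: stage 1 n = 17, continue at 4 or fewer complications; stage 2 n = 22; success at 7 or fewer of 39; null rate 0.31; alternative 0.14.

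P(success) = Σ over x = 0 to 4 of P(X1 = x) × P(X2 ≤ 7 − x). At 0.31:

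| x | P(X1 = x) | P(X2 ≤ 7 − x) | product |
|---|---|---|---|
| 0 | 0.0018 | 0.6327 | 0.0012 |
| 1 | 0.0139 | 0.4532 | 0.0063 |
| 2 | 0.0500 | 0.2784 | 0.0139 |
| 3 | 0.1123 | 0.1411 | 0.0159 |
| 4 | 0.1766 | 0.0562 | 0.0099 |

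The unrounded sum is 0.0471 (stated: approximately 0.05). Power at 0.14 is 0.805 (stated 0.80). P(X1 ≥ 5) at 0.31 is 0.6453 (stated 0.6453). The design reproduces.

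**3. Primary endpoint, mild case.** Assume that one patient per trial is withdrawn and counted complication-free whatever happens to her, so one patient can no longer contribute an event.
- In stage 2 (22 becomes 21): type I error 0.057.
- In stage 1 (17 becomes 16): type I error 0.058.

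**4. Primary endpoint, extreme case.** Assume that one true complication is lost in every trial.
- Lost in stage 2: success needs X1 ≤ 4 and a true total ≤ 8. P(X1 ≤ 4, total exactly 8) = 0.0419, so 0.0471 + 0.0419, or 0.089 from unrounded terms.
- Lost in stage 1: a true 5 of 17 also reads as 4 and passes. This adds P(X1 = 5) × P(X2 ≤ 3) = 0.2063 × 0.0562 = 0.0116, giving 0.0891 + 0.0116 = 0.1007, or 0.101.

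**5. Survival.** Assume 4 deaths among 39 by five years: 1 − 4/39 = 89.7%. Patients withdrawn before death are censored. The Kaplan-Meier result depends on whether censoring falls after or before the observed deaths.
- None hidden: 89.7%.
- One hidden: 1 − 3/39 = 92.3% (censored after) to 1 − 3/38 = 92.1% (censored before).
- Two hidden: 1 − 2/39 = 94.9% to 1 − 2/37 = 94.6%.

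The death count and the hidden share are assumptions; the documents give neither. The same arithmetic applies to local recurrence.

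**The case against.** The best case for the plan has four parts.

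First, decline alone is not enough; withdrawal must also serve the patient. After five fractions and surgery, what remains is mainly visits, questionnaires, photographs and mammograms, so there is little to withdraw her from. The protocol itself expects few such cases. This stands as a limit on frequency, but the text still permits withdrawal at any time.

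Second, the recurrence or complication behind a decline would usually have been recorded already, and is kept. This stands. The clearest loss is death after withdrawal, together with first events that come later.

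Third, 5.3.4 speaks of a patient who withdraws, which might mean only her own choice. This is weak: 5.3.3 uses both forms for the same cases, and there is no other data rule for withdrawal by physicians.

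Fourth, no success decision rests on survival or local control. This stands, and it limits the consequence.

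A reader might infer more than the text supports: that outcomes are in fact being lost in the patients doing worst, that eligibility withdrawals are the sickest patients, or that 11.2 commits overall survival to Kaplan-Meier. The first is a possibility under a permissive rule. The second does not follow from an eligibility violation. On the third, overall survival is a listed endpoint, but it is missing from the outcomes that 11.2 names for those methods, so the point for survival rests on 5.3.4 and objective 2.2.5.

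**Conclusion.** The concern holds in a limited form. Sections 5.3.2 and 5.3.4 together create informative censoring by rule, and 5.3.5 does not repair it. The main exposure is local control, fibrosis, pain and recorded survival, all in the favourable direction. The primary endpoint is exposed only when a patient is withdrawn after radiation and has a first complication afterwards, within 3 months of surgery.

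The size cannot be estimated from the documents, because no rate of withdrawal after treatment is given. The type I error figures (0.057–0.058, and 0.089 or 0.101) assume that a withdrawn patient is counted as complication-free; the last two also assume a lost event in every trial. They show sensitivity and are not forecasts. It would be wrong to read them as saying that the stated error rate is miscalculated, since it reproduces, or to take 0.089 as a ceiling, since a loss in stage 1 gives 0.101. The change is worth making because it is cheap and because one or two patients matter among 39.

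**What to change.** Amend 5.3.2 and 5.3.4 to separate leaving protocol procedures from leaving data collection:
- In a treated patient, a physician's decision or a late eligibility finding ends protocol procedures only. The clinical grounds for that decision stay as they are.
- Complications to 3 months after surgery, recurrence, late toxicity and vital status continue to be collected from the chart and are used in all analyses.
- Only the patient's own withdrawal of consent to data collection stops the use of later data.
- Treated patients found ineligible stay in the primary count, with a sensitivity analysis that excludes them.

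The cost is protocol and consent wording, limited chart review, and possibly a few ineligible patients in the main analysis. Sample size, decision rule and treatment do not change. Section 5.3.5 already sets a minimum of clinical follow-up, so most of the records should exist.

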8.0 Surgery and Post-Operative Treatment

8.1 Breast conserving surgery

Breast conserving surgery (lumpectomy) and sentinel node biopsy will occur no sooner than 5 weeks following completion of RT, but should occur no later than 8 weeks. In patients with rectal cancer, this interval has been shown to produce optimal response to pre-operative radiation while maintaining low rates of post-operative complications (101). Surgical techniques such as needle localization will be performed at the discretion of the treating surgeon and in concordance with current standard of care. Oncoplastic procedures are discouraged, but will not be counted as a protocol violation or removal from the study.

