11.0 Statistical Considerations

11.1 Sample Size, Power Calculations, and Comparison of Post-Operative Complications to Historical Controls

The primary endpoint of this study will be post-operative complications (as defined in section 10.1.4). The complication rate measured on this study will be compared to a historical control of 32% of patients, as outlined in section 1.6. This will be measured on an individual patient level. Hence a surgical complication rate that exceeds 31% will be considered unacceptable and result in a negative study. A post-op complication rate of 14% or less will be considered a successful demonstration of the safety of this treatment. This number was selected because it is roughly half the complication rate observed on the study by Horton et.al. (94) and represents an increase in complication rate of only 8% over that reported by Boostrom et.al. (102). To demonstrate this, a Simon's two stage design (104) will be used for this study. The value of this approach is that in stage 1 it can be demonstrated that pre-operative APBI using this dose and fractionation scheme is not excessively risky. Once that condition is satisfied, stage 2 is then used to demonstrate that it meets a better standard of complications compared to the Horton study with only a modest increase in complications when compared with historical series of complications observed without pre-operative radiation therapy.

For this analysis we assume as a null hypothesis that the true complication rate is 0.31. This will be tested against a one-sided alternative. In stage one of accrual, 17 patients will be enrolled. If there are 5 or more complications in these 17 patients, enrollment will be suspended and the study will be evaluated for possible closure. This will serve as the stopping rules for the study under the null hypothesis of a 31% complication rate. Otherwise, 22 additional patients will be accrued (total 39) in stage two, and the null hypothesis will be rejected if there are 7 or fewer complications among the 39 total. This design yields a type I error rate of approximately 0.05 and power of 0.80 when the true complication rate is 14%. With this design, the probability of stopping early is 0.6453. To allow for possible withdrawal prior start of treatment or other unforeseen problem with enrollment, total enrollment will be 40 patients.

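### Section 5.3.4 lets the outcome decide whether a patient who withdraws during radiation is in the primary analysis, and does not fit the sentence before it (minor; wrong as written)

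*Combined protocol and SAP*

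**What the plan says.** Section 5.3.4 has two sentences on withdrawal after treatment has started. The first is general: "only data collected up until the date of withdrawal will be used in analysis". The second covers withdrawal during radiation and the primary endpoint only: "data will only be included in analysis of the primary study endpoint if a post-operative complication occurs".

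Other sections bear on it:

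- **5.3.1:** "it is unlikely that patients will withdraw from the study once radiation treatment has begun". No rate is given.
- **5.3.3:** replacement is stated for withdrawal before treatment ("patients withdrawing for any other reason prior to delivery of treatment will be replaced on the study"). Nothing is said about replacing treated patients.
- **5.3.5:** after withdrawal, "Follow-up will be per the discretion of the patient's treating physicians", with national guidelines as the minimum.
- **8.1:** "Breast conserving surgery (lumpectomy) and sentinel node biopsy will occur no sooner than 5 weeks following completion of RT".
- **8.2:** sentinel node biopsy should accompany the lumpectomy but may be done before radiation.
- **10.1.4:** the primary endpoint "will be defined as any complication occurring within 3 months of surgery".
- **11.1:** stage 1 has 17 patients and pauses at 5 or more complications. At the end, "the null hypothesis will be rejected if there are 7 or fewer complications among the 39 total". Enrolment is 40. No evaluable set is defined.

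**The concern.** The set on which a rate is estimated should be fixed without looking at the outcome. The second sentence of 5.3.4 admits a patient because she had the event and omits her because she did not. The trial is single-arm and its primary aim is to determine that rate.

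The sentence also conflicts with the one before it. If data stop at the date of withdrawal, and withdrawal falls during radiation, lumpectomy is still at least 5 weeks away and no lumpectomy complication can be on record. Either the second sentence overrides the first or it is nearly empty. Sections 5.3.3, 10.1.4 and 11.1 do not say which. The two readings have different consequences: one distorts the reported percentage, the other can reduce the number analysed below the 39 for which the cut-off was set.

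**Working it through.** **Inputs.** Section 11.1: null rate 0.31, alternative 0.14, one-sided; n1 = 17, continue with 4 or fewer complications; n = 39, reject with 7 or fewer. Timing is from 8.1 and the endpoint window from 10.1.4. The number of withdrawals is not given, so 1 to 3 are shown as assumptions.

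**Step 1: the plan's own figures.** With b the binomial probability and B its cumulative sum,

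P(reject | p) = Σ over x1 = 0 to 4 of b(x1; n1, p) × B(7 − x1; n − n1, p).

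For 17/39 this gives type I error 0.0471 at p = 0.31 and power 0.8050 at p = 0.14. The chance of early stopping under the null is 0.6453. These agree with section 11.1 (approximately 0.05, 0.80 and 0.6453).

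**Step 2: second sentence read as an exception, no replacement, later complications fully ascertained.** Of N treated, k withdraw during radiation. X1 ~ Bin(N − k, p) counts events among the others and X2 ~ Bin(k, p) among the withdrawers. The reported rate is (X1 + X2)/(N − k + X2). The numerator is the same as with everyone included, so the comparison with 7 is unchanged; only the denominator shrinks.

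For k = 1 the expectation is (1 − p)p + p[(N − 1)p + 1]/N. With N = 40:

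- p = 0.14: 0.86 × 0.14 + 0.14 × (39 × 0.14 + 1)/40 = 0.1204 + 0.0226 = 0.1430.
- p = 0.31: 0.69 × 0.31 + 0.31 × (39 × 0.31 + 1)/40 = 0.2139 + 0.1015 = 0.3153 (terms rounded).

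Two withdrawers give 0.1462 and 0.3209. With N = 39, one withdrawer gives 0.1431 and 0.3155. The shift is about 0.3 points per withdrawer at 14% and about 0.5 at 31%, upward.

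If excluded patients were replaced, which the protocol does not provide for, the event probability per analysed patient would be p/[(1 − w) + wp], where w is the withdrawal probability. At an assumed w of 2.5%, 5% and 10%, type I error would be 0.041, 0.035 and 0.025, and power 0.789, 0.772 and 0.734.

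**Step 3: first sentence governs.** Withdrawal during radiation precedes lumpectomy by more than 5 weeks, so no lumpectomy complication is in the data and these patients leave the analysis. The possible exception is a complication of a sentinel node biopsy done before radiation, if that procedure counts as surgery under 10.1.4. She would again be included because of her event.

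Assume all 40 places are treated, no replacement, cut-off kept at 7, and no such exception. Ranges cover how many losses fall in stage 1:

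| Losses | Analysed | Type I error | Power |
|---|---|---|---|
| 1 | 39 | 0.047 to 0.048 | 0.805 to 0.811 |
| 2 | 38 | 0.057 to 0.059 | 0.820 to 0.832 |
| 3 | 37 | 0.068 to 0.072 | 0.834 to 0.852 |

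Lowering the cut-off to 6 gives type I error 0.026 and power 0.712 to 0.717 at 38, and 0.032 to 0.033 with 0.733 to 0.741 at 37.

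**Step 4: one patient of unknown status among 39.** Counted as event-free, she gives type I error 0.057 (stage 2) or 0.058 (stage 1). Counted as a complication, she gives 0.026 with power 0.712 (stage 2), or 0.023 with power 0.670 (stage 1).

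**The case against.** The second sentence is narrower than the first, so it reads most naturally as a specific exception to a general rule. On that reading no decision based on the count changes, the shift is a fraction of a point per withdrawer, and it goes against the treatment. Counting known harm while giving no safety credit for incomplete radiation can be defended in a safety trial. Type I error above 0.05 arises only on the other reading and, with 40 treated, only after two losses in a treatment course of about two weeks.

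Most of this stands, and it is why the point is minor. It does not settle the matter. The text does not say which sentence governs, and a conservative direction does not make an outcome-dependent set a sound basis for estimating a rate. The unchanged decision also requires that complications after withdrawal are found. Section 5.3.5 leaves follow-up to the treating physicians, and a missed event would lower the count.

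Three stronger readings are tempting and are not supported:

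- **The rule makes the treatment look safer.** As an exception with complete ascertainment, it does the reverse.
- **The rule inflates type I error in general.** It does so only if the first sentence governs, the cut-off stays at 7 and fewer than 39 remain.
- **The second sentence can never apply if the first governs.** Section 8.2 allows sentinel node biopsy before radiation, so a complication of that biopsy could be on record at withdrawal.

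**Conclusion.** The rule is wrong as written, and the fault is minor. Section 5.3.4 selects on the outcome for patients who withdraw during radiation, contradicts its own preceding sentence, and is not resolved elsewhere in the document.

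On the more natural reading, with complete ascertainment and no replacement, the damage is confined to the reported percentage. On the other reading, two or three losses among 40 treated move type I error from 0.047 to between 0.057 and 0.072 if the cut-off is kept. Both sizes rest on assumed numbers of withdrawals. If withdrawal after treatment starts is as rare as 5.3.1 and 5.3.4 expect, the practical effect is small. A reader should not infer that the trial's conclusion is at risk from this sentence alone.

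**What to change.** - **5.3.4:** replace both sentences as they apply to the primary endpoint. Define the primary set without reference to outcome, for example all patients who receive at least one fraction and then have the breast conserving surgery of section 8.1. This also covers patients who leave between radiation and surgery. Allow 3-month complication status to be taken from existing clinical records after withdrawal where consent permits, as an explicit exception to the data cut-off. Deleting only the second sentence would leave that cut-off in place and block the record search.
- **10.1.4:** state whether a sentinel node biopsy done before radiation counts as surgery for the endpoint.
- **5.3.3 and 11.1:** state whether treated patients who never have the breast conserving surgery are replaced. State that if the final number is not 39, the cut-off is recomputed or the exact type I error is reported.
- **Unknown status within the set:** report the result both ways, event-free and as a complication, with the error rates of step 4. Neither should be presented as neutral: the first has the same type I error as excluding the patient, and the second costs power.

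The cost is a rewritten paragraph, a few sentences, a little record review and one extra sensitivity analysis. Lowering the cut-off to 6 at 38 patients would cost about 9 points of power (0.805 − 0.717 = 0.088 to 0.805 − 0.712 = 0.093).
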